9.8.3. Barnes Akathisia Rating Scale (BARS)

BARS is used to assess the severity of drug-induced akathisia. Objective Akathisia, Subjective Awareness of Restlessness and Subjective Distress Related to Restlessness in the scale measure the level of subject's restlessness, ranging from zero (normal) to 3 (most severe) and are summed yielding a total score ranging from 0 to 9. The BARS also includes a global clinical assessment of akathisia, ranging from zero (absent) to 5 (severe).

The objective, subjective, total of objective and subjective scores and global scores will be summarized at Baseline and every month during treatment for one year. All questionnaire data will be displayed in a listing.

9.8.4. Children's Depression Rating Scale-Revised (CDRS-R)

CDRS-R is a clinically validated rating scale designed to assess psychiatric signs and symptoms of depressions in children and adolescents. Fourteen signs and symptoms are rated from 1 (normal) to 7 (most severe), and 3 signs and symptoms are rated from 1 (normal) to 5 (most severe). The raw summary score is the sum of all 17 items, ranging from 17 to 113.

The raw summary score will be summarized at Baseline and every month during treatment for one year. All questionnaire data will be displayed in a listing.

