8.3. Subject Withdrawal Criteria

The Investigator or subject themselves may stop study treatment at any time for safety or personal reasons.

Any subject with a CDRS-R assessment indicative of the onset of a new depressive episode at any visit can be discontinued from study participation at the discretion of the Investigator. Any subject with a new positive response on questions 4 and/or 5 of the C-SSRS will be immediately discontinued and evaluated for risk. Dosing may be restarted at the discretion of the Investigator following consultation with the Sponsor or its designee.

Where possible, a subject who discontinues treatment will undergo the protocol-specified end-of study procedures at the time of discontinuation. Date and reason(s) of premature discontinuation will be described on the CRF. In addition, the date of last dose of study treatment will be recorded on the Study Treatment Dosing CRF.

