4.3. Other Safety Endpoints

- Changes from baseline in Columbia Suicide Severity Rating Scale (C-SSRS) results.
- Changes from baseline in Abnormal Involuntary Movement Scale (AIMS) results.
- Changes from baseline in Barnes Akathisia Rating Scale (BARS) results.
- Changes from baseline in Children's Depression Rating Scale-Revised (CDRS-R) results.
- Changes from baseline in Pediatric Anxiety Rating Scale (PARS) results.

This document is confidential.

5. Analysis Sets

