6.2. Key Definitions

Treatment emergent adverse events (TEAEs) are defined as any adverse events that start or increase in intensity on or after the first dose of open-label treatment on Day 1.

Duration of exposure is defined as (Date of Last Dose – Date of First Dose) +1. If date of last dose is unknown, then the date of last clinical visit will be used to impute the date of last dose.

Baseline is defined as the last measurement taken before the first dose of open-label treatment on Day 1.

Change from baseline will be calculated for the post-baseline assessment as post-baseline value – baseline value.

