9.8.2. Abnormal Involuntary Movement Scale (AIMS)

AIMS records the occurrences of tardive dyskinesia (TD) in subjects receiving neuroleptic medications. The test is used to detect TD and to follow the severity over time. It consists of rating the presence and severity of movement disorders involving the face, mouth, extremities, and trunk as well as three items of global judgment from a scale of 0 (none) to 4 (severe).

The AIMS total score will be calculated by summing the severity of the 10 items that are rated on a scale of 0 to 4. The total score will be summarized at Baseline, Months 1, 2, 3, 4, 5, 6, 7, 8, 9, 10, 11 and 12.

All questionnaire data will be displayed in a listing.

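### AIMS, BARS, CDRS-R and PARS are defined as change-from-baseline endpoints, but the SAP plans only by-visit score summaries, in which an early-termination score counts in one monthly mean and in none after it

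*SAP*

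**What the plan says.** SAP 4.3 lists the AIMS endpoint as "Changes from baseline in Abnormal Involuntary Movement Scale (AIMS) results" and the CDRS-R endpoint as "Changes from baseline in Children's Depression Rating Scale-Revised (CDRS-R) results"; those for BARS and PARS take the same form. SAP 6.2 gives a general rule ("Change from baseline will be calculated for the post-baseline assessment", by subtracting the baseline value) but does not say which scales will be tabulated that way.

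The analysis text is in SAP 9.8.2–9.8.5. For AIMS, "The total score will be summarized at Baseline, Months 1, 2, 3, 4, 5, 6, 7, 8, 9, 10, 11 and 12". For CDRS-R, "The raw summary score will be summarized at Baseline and every month during treatment for one year". The BARS and PARS sections likewise plan summaries of the scores at Baseline and monthly. None of the four sections mentions change.

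Three other provisions decide which scores enter each monthly mean:

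- SAP 6.4, repeated in Section 10, covers every efficacy and safety scale. It assigns an Early Termination (ET) assessment to the next visit scheduled for that scale after the subject's last scheduled visit.
- SAP 6.1 puts unscheduled visits in the listings only.
- Protocol 8.3 gives the Investigator discretion over withdrawal on this scale: anyone whose CDRS-R result is "indicative of the onset of a new depressive episode at any visit can be discontinued from study participation". It asks for end-of-study procedures at discontinuation only where they can be done.

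**The concern.** Safety and tolerability is the primary objective and there is no control arm, so comparison with baseline is the main way these scales can show harm. The scales also cover a known risk. Protocol 5.2.2.1 reports that the Phase 3 obesity studies were stopped for psychiatric events (31% on ecopipam against 15% on placebo), with depression and anxiety about twice as frequent as on placebo.

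Two things follow if Section 9.8 is carried out as written. First, the endpoint in 4.3 is never tabulated. Second, a reader who compares the Baseline mean with the Month 12 mean compares everyone with those still in the study. For CDRS-R, remaining in the study can depend on the score itself.

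**Working it through.** **1. Does the SAP plan change elsewhere?** Yes, explicitly: for YGTSS (8.1), CGI-TS-S (8.2), C&A-GTS-QOL (8.3), laboratory tests (9.4), vital signs (9.5) and ECG (9.6). Its absence from all four of 9.8.2–9.8.5 is therefore a gap in the analysis text. Two features are not evidence of the gap. Raw summary score is simply the SAP's name for the 17-item CDRS-R sum. The titles of Tables 14.3.4.5.2–14.3.4.5.5 omit change, but so do the titles for YGTSS-TTS, CGI-TS-S and vital signs, where change is planned.

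**2. Where does a withdrawal score go?** All four scales are scheduled monthly. Under 6.4, a subject last seen at Month 3 who has an ET assessment contributes it to Month 4. No rule carries it to Month 5 or beyond, although the approach is labelled a modified LOCF.

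**3. Size of the effect on the means.** The documents give no sample size, dropout rate or SD for these scales, so there is no planned figure to reproduce. All inputs here are assumptions:

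- those who stay are flat at 25 points;
- a share f worsens by D points after the Month 3 visit and withdraws;
- a share c of those has an ET assessment.

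Month 4 shift = f·c·D / [(1 − f) + f·c]

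With f = 10% and D = 20:

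| c | Month 4 shift | Months 5–12 shift |
|---|---|---|
| 100% | 0.10 × 1 × 20 / (0.90 + 0.10) = 2.00 | 0.00 |
| 50% | 0.10 × 0.5 × 20 / (0.90 + 0.05) = 1.05 | 0.00 |
| 0% | 0.00 | 0.00 |

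With c = 100%, across f = 5–20% and D = 10–30, the Month 4 shift runs from 0.05 × 10 = 0.50 to 0.20 × 30 = 6.00. It is 0.00 at every later visit.

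**4. What a per-subject last change would show.** Over all subjects the mean is f·c·D, if those without an ET assessment contribute a Month 3 score equal to baseline. With f = 10% and D = 20, that is 2.00 at c = 100% and 0.10 × 0.5 × 20 = 1.00 at c = 50%. It does not fade at later visits, but it cannot recover worsening that nobody assessed.

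**5. Drift from composition alone.** Suppose 10% leave, their baseline was 10 points higher, and no subject changes. The Baseline mean is 0.90 × 25 + 0.10 × 35 = 26.00 and the later mean is 25.00. The apparent improvement is 1.00 point, while the paired change is 0. With 5–20% leaving and baselines 5–20 points higher, the apparent improvement runs from 0.25 to 4.00 points.

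**The case against.** A reader might infer that worsening which leads to withdrawal vanishes from the means altogether. The documents do not support that. SAP 6.4 puts the ET score of every safety scale into the next scheduled mean. If the CDRS-R assessment that prompts withdrawal was made at a scheduled visit, that score is already in that visit's mean. Worsening is missed entirely only if it was assessed at neither a scheduled nor an ET visit, or was recorded only at an unscheduled one. No figure shows how often the discretionary rule in Protocol 8.3 is used.

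Nor do the documents show a decision not to analyse change. With 4.3 naming it and 6.2 defining it, incomplete drafting of 9.8 is the more natural explanation.

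The case against also notes that worsening can surface elsewhere: in adverse events leading to treatment termination, in the special-interest category for depression and suicide or self-injury, in the C-SSRS summaries, and in the questionnaire listings. That is true and limits the harm. But adverse events depend on being reported, listings give no incidence, and 4.3 makes change on each scale an endpoint in its own right.

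Finally, paired change by visit would not bring back subjects who have left. This is also correct: it removes composition drift only. The per-subject summaries are what keep leavers in view.

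**Conclusion.** The mismatch is real for all four scales: 4.3 defines change from baseline and 9.8.2–9.8.5 do not tabulate it. Worsening first recorded at an ET visit counts in one monthly mean and is absent from all later means, including Month 12. Comparing Baseline with later means therefore compares different, possibly selected groups.

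The mismatch rests on the text alone. The sizes rest on assumed inputs: with full ET capture, 0.50 to 6.00 points in one month and 0.00 afterwards. They show the mechanism and do not predict the result. Staggered withdrawals would spread these contributions over several months and make each smaller. The summaries are descriptive and no hypothesis test depends on them, so this is a worthwhile, inexpensive correction to the safety reporting. It does not invalidate the analysis.

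**What to change.** In SAP 9.8.2–9.8.5 and the shells for Tables 14.3.4.5.2–14.3.4.5.5:

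1. Add paired change from baseline at each visit, for subjects with both values. This delivers the 4.3 endpoint and removes composition drift.
2. Add each subject's last and maximum post-baseline change, using all assessments including ET and unscheduled ones. Report the number and percentage with any increase from baseline and the distribution of the maximum change. The SAP sets no worsening threshold for these scales, so the distribution matters more than any single cut.
3. Label the last-change and maximum-change summaries post hoc and record them in Section 10, which shows that the SAP was already being changed after database lock. The ET rule is itself one of those late changes.

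The cost is a few table rows and the programming; no new data are needed. The maximum will tend to look less favourable than the visit means because it picks the highest of up to a year of monthly measurements, and a footnote should say so.

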9.8.5. Pediatric Anxiety Rating Scale (PARS)

PARS is a clinician-rated instrument for assessing the severity of anxiety symptoms associated with common anxiety disorders and generalized anxiety in children and adolescents. PARS is a 7-item scale that is used to determine severity of symptoms and the PARS total score. Each severity item is coded

This document is confidential.

from zero (none) to 5 (most extreme). Not applicable is coded to 8 and does not know is coded to 9. The total score for the PARS is total of the 7 severity items. The total score ranges from 0 to 35. Codes “8” and “9” are not included in the summation.

The total score will be summarized at Baseline and every month during treatment for one year. All questionnaire data will be displayed in a listing.

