Scores for the six subscales are generated by summing items and, for ease of interpretation, transformation to a range of 0 to 100 ($100 \times [(observed\ score - min\ possible\ score) / (max\ possible\ score - min\ possible\ score)]$). The total score, resulting from the sum of the subscale scores, is also normalized to a 0–100 range. For C&A GTS-QOL, if a response to 1 question is missing within the subscale, the missing response will be replaced with the average of the remaining responses within the subscale; if responses to 2 or more questions within a subscale are missing, the missing responses will not be replaced and the subscale score will be set to missing; if at least 1 subscale is missing then the total score will be set to missing. For all analysis and summary, transformed scores will be used.

Summary statistics for the overall VAS score, QOL subscale scores for Cognitive, Psychological, Obsessive-compulsive, Physical, Coprophenomena, and ADL and QOL total score will be presented along with a full data listing by visit. The paired t-test will be used for analyzing the change from baseline within treatment. Mean C&A-GTS-QOL Change from Baseline Total Score and VAS Change from Baseline Score Over Time will be illustrated in a figure.

This document is confidential.

9. Safety

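### SAP 9.8.5 drops PARS items coded 9 (does not know) from an unscaled sum, which scores unknown anxiety as none

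*SAP*

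**What the plan says.** SAP 9.8.5 defines the score as a plain sum: "The total score for the PARS is total of the 7 severity items". Each item runs from 0 (none) to 5, and the section states the resulting scale: "The total score ranges from 0 to 35". Two codes lie outside the severity scale: "Not applicable is coded to 8 and does not know is coded to 9". Their handling takes one sentence: "Codes “8” and “9” are not included in the summation". The section does not say whether the sum is then rescaled, how many rated items are needed, or when the total becomes missing.

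On use of the score, SAP 9.8.5 says: "The total score will be summarized at Baseline and every month during treatment for one year". SAP 4.3 lists the endpoint as "Changes from baseline in Pediatric Anxiety Rating Scale (PARS) results".

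Nothing elsewhere fills the gap:
- SAP 6.3 (Missing Data) deals only with partial dates.
- The modified LOCF in SAP 6.4 reassigns whole Early Termination visits and does not touch items.
- Protocol 12.1 describes the PARS, and Protocol 13.2.1 sets out the safety analysis. Neither gives a scoring rule.

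For another scale the SAP does set an item-level rule. In SAP 8.3 (C&A-GTS-QOL), when one item of a subscale is unanswered, "the missing response will be replaced with the average of the remaining responses within the subscale". With two or more unanswered, the subscale score is set to missing.

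**The concern.** Codes 8 and 9 mean different things. Not applicable may legitimately add nothing to a severity total. Does not know says that the severity exists but was not established. The SAP treats the two alike, and on a total still read against 0 to 35 the unknown item takes the value that the scale reserves for no symptom.

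The primary objective of the study is long-term safety, and there is no control arm, so the PARS evidence is the course of the score over time. Anxiety is a known question for this drug. Protocol 5.2.2.1 reports that the Phase 3 obesity studies were discontinued for psychiatric adverse events including anxiety. It also reports anxiety in 14% (211/1482) of subjects on ecopipam, about twice the frequency on placebo. If the use of code 9 shifts between baseline and later visits, the PARS means will move for a reason unrelated to anxiety.

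**Working it through.** **Inputs.** From SAP 9.8.5: 7 items, each rated 0 to 5; codes 8 and 9 left out of the sum; stated range 0 to 35. All item scores and code 9 rates below are assumptions, because the documents give none.

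**1. The plan's own figure.** Minimum 7 × 0 = 0; maximum 7 × 5 = 35. The stated range is reproduced, but only when all seven items carry a 0 to 5 rating.

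**2. Effect on one visit's total.** With k items coded 9 and none coded 8, the attainable maximum is 5 × (7 − k): 30, 25 and 20 for k = 1, 2 and 3. The as-stated total equals the true total minus the true values of the k unknown items, so each code 9 removes between 0 and 5 points. If every item is truly 3 (true total 7 × 3 = 21):

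| Code 9s | As stated | Shortfall | Prorated, × 7/(7 − k) |
|---|---|---|---|
| 1 | 6 × 3 = 18 | 3 (14.3%) | 18 × 7/6 = 21 |
| 2 | 5 × 3 = 15 | 6 (28.6%) | 15 × 7/5 = 21 |
| 3 | 4 × 3 = 12 | 9 (42.9%) | 12 × 7/4 = 21 |

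The shortfall is k/7 of the true total whenever the unknown items match the mean of the rated ones. Proration recovers the true total only under that same condition.

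**3. Effect on change from baseline.** Let U(b) and U(v) be the summed true values of the items coded 9 at baseline and at the later visit. Then:

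as-stated change = true change + U(b) − U(v)

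- *Code 9 only at the later visit.* Baseline all 2s = 14; later visit truly all 3s = 21; true change +7. With two code 9s later: 15 − 14 = +1. With three: 12 − 14 = −2, an apparent improvement.
- *Code 9 only at baseline.* All items truly 2 at both visits, true change 0. With two code 9s at baseline: 14 − (5 × 2) = +4, an apparent worsening.
- *Two code 9s at both visits.* No true change, all 2s: 10 − 10 = 0. A true rise from all 2s to all 3s: 15 − 10 = +5 instead of +7. Equal use cancels when nothing changes and shrinks a real change.

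**4. Group-level size, on assumed rates.** Suppose each item is coded 9 with probability p, independently of the other items and of its own severity, with mean item score m and no code 8s. The share of assessments with at least one code 9 is 1 − (1 − p)^7, and the mean shortfall is 7 × p × m.

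| p | At least one code 9 | Shortfall, m = 2 | Shortfall, m = 3 |
|---|---|---|---|
| 2% | 13% | 0.28 | 0.42 |
| 5% | 30% | 0.70 | 1.05 |
| 10% | 52% | 1.40 | 2.10 |

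The true mean total is 7 × m, so the relative shortfall is simply p. If code 9 is hardly used, the effect is close to nil.

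**The case against.** The strongest reply is that the consequence is limited. PARS is one of the other safety endpoints, summarized descriptively, with no test or cut-off attached. The score-based withdrawal provisions in Protocol 8.3 use the CDRS-R and the C-SSRS, not the PARS. Anxiety is also captured by adverse event reporting at every visit, and anxiety is one of the AESI terms in SAP 9.3. The obesity-programme signal was itself an adverse event signal, and the scoring rule does not affect that route. Questionnaire data are listed (Listing 16.2.8.9), so affected totals can be traced. All of this stands and bears on priority. It does not correct the means in Table 14.3.4.5.5.

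It may also be that the plain sum is the instrument's own convention. The scale's source is cited but cannot be consulted here, so this stays open. It is a reason to keep the as-stated total visible.

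A fair objection applies to simply borrowing the SAP 8.3 rule. If two code 9s set the only reported total to missing, a child rated 5 on five items leaves the visit summary, although 5 × 5 = 25 is a valid lower bound. Mean replacement also needs a definition when code 8 is present. Both points stand and shape the fix.

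Three stronger readings are tempting and not supported:
- *That the rule always errs towards apparent safety.* It can never raise a single-visit total, but the endpoint is change from baseline, where the error can go either way.
- *That a child with all seven items coded 9 scores 0, the best possible value.* The SAP does not say what happens when nothing is left to sum; a missing total is equally possible.
- *That remote visits would inflate code 9.* Remote administration is allowed, but nothing in the documents links it to code 9.

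**Conclusion.** The point holds as a scoring defect of unknown practical size. As written, a does-not-know rating enters the PARS total as 0, and no other section repairs this. The single-visit error is 0 to 5 points per code 9, always downward or nil. The error in change from baseline is U(b) − U(v). Where unknown items are of similar severity at both visits, it leans towards improvement if code 9 is more frequent after baseline and towards worsening if it is more frequent at baseline.

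The group-level effect rests wholly on the frequency of code 9. The range of 0.28 to 2.10 points is what item rates of 2% to 10% and mean item scores of 2 to 3 would give, not an estimate for this trial; the true figure may be smaller. The change is worth making because it is cheap and because the per-visit counts would show whether the issue matters. The documents do not support a claim that the PARS results are biased towards safety overall.

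**What to change.** In SAP 9.8.5:

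1. Separate the two codes. Keep code 8 as stated (it adds nothing to the sum) and define code 9 as missing.
2. Derive a prorated total by replacing each code 9 with the mean of that subject's items rated 0 to 5 at the same visit. With S the sum of the rated items, r their number and u the number of code 9s, the prorated total is S + u × S/r. For example, two items rated 3, one code 9 and four code 8s give 6 as stated and 6 + 3 = 9 prorated.
3. State a limit on u, for example one, as in SAP 8.3. Set the prorated total to missing beyond the limit or when no item is rated 0 to 5.
4. In Table 14.3.4.5.5, show the prorated and as-stated totals side by side, so that no child with high rated items drops out of the summary. Add the number of assessments with any code 9 at each visit.
5. Record the change in SAP Section 10, which already lists updates made after database lock, so that its timing is open.

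The cost is one extra derivation, a departure from the simple sum in one row, and some prorated totals set to missing. It is also one more post-lock change. No new data are needed, since the questionnaire data are already collected and listed.

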9.9. COVID-19 Analyses

Due to COVID-19 pandemic, additional analyses will be conducted:

- Listings of COVID-19 related study disruptions by subject and by site, including descriptions of the disruption.
- Protocol deviations due to COVID-19 will be summarized by type in a table.

This document is confidential.

10. Changes from Analysis Planned in Protocol

As per protocol, the Modified Intention-to-Treat (mITT) set was defined as all subjects who receive at least one dose of study drug which is same as the safety population set. Hence the mITT set definition was updated as 'all subjects who receive at least one dose of study drug and have at least one post Baseline scoring of YGTSS'.

Following updates and additional analysis were included in the SAP after the data base lock.

- An additional analysis set, Intention-to-Treat (ITT) Set, was defined as all enrolled subjects. All efficacy analysis will also be conducted using the ITT population.
- Visit windowing will be used in the summarization or analysis of safety laboratory, vital signs, ECG, and physical exam data.
- For all efficacy and safety scales a modified last observation carried forward (LOCF) approach will be used to reassign Early Termination visits. Early Termination visits will be assigned to the next scheduled visit (per Schedule of Assessments for the parameter) after a subjects' latest scheduled visit before early termination.
- Demographics and baseline characteristics will also be summarized by treatment group (ecopipam, placebo, overall) from CL (EBS-101-CL-001) study in the mITT Set (Table 14.1.3.1a), and be also summarized for the ITT Set (Table 14.1.3.1b).
- Medical history will also be summarized by treatment group (ecopipam, placebo, overall) from CL (EBS-101-CL-001) study in the Safety Set (Table 14.1.3.2a).
- Extent of exposure summary by days will be provided as well (Table 14.1.5a).
- YGTSS-TTS will also be summarized by treatment group (ecopipam, placebo and overall) from CL (EBS-101-CL-001) study (Tables 14.2.1.1.1a).
- Efficacy summaries for the ITT Set will be generated (Tables 14.2.1.1.1b, 14.2.1.1.2b, 14.2.1.1.3b, 14.2.1.1.4b, 14.2.1.2b, 14.2.1.3b, and 14.2.1.4b).
- A summary of the percent of subjects with a 25% or greater improvement on the YGTSS-TTS in mITT set will be provided (Table 14.2.1.1.5).
- A summary of the most common ($\geq 5\%$) AEs first onset by month will be provided in Table 14.3.1.9.1 and by month (new incidence or ongoing) in Table 14.3.1.9.2.
- Shifts from baseline summaries in BMI z-score, height z-score, and weight z-score will be generated and provided in Table 14.3.4.6a, Table 14.3.4.6b, and Table 14.3.4.6c, respectively. Mean BMI, height, and weight z-scores over time will be illustrated in Figure 14.3.4.6a, Figure 14.3.4.6b, and Figure 14.3.4.6c, respectively.
- A summary of shifts from baseline in 12-lead ECG QTc will be provided in Table 14.3.4.7a. A summary of outliers in 12-lead ECG will be provided in Table 14.3.4.7b.
- A summary of heart rate outliers will be provided in Table 14.3.4.7c.
- Shifts from baseline in HbA1c and total cholesterol will be provided in Table 14.3.4.8 and Table 14.3.4.9, respectively.

This document is confidential.

- Generation of listings for ITT Set: Listing 16.2.4.1b (demographics and baseline characteristics), Listing 16.2.6.1b (YGTSS), Listing 16.2.6.2b (CGI-TS), and Listing 16.2.6.3b (C&A-GTS-QOL).
- Generation of listings for Safety Set: Listing 16.2.9.1 (Height, Weight, and BMI z-scores).
- Generation of figures: mean changes from baseline for C&A-GTS-QOL total score (Figure 14.2.1.4.1a), mean changes from baseline for C&A-GTS-QOL VAS (Figure 14.2.1.4.1b), mean BMI, Height, Weight z-scores over time (Figures 14.3.4.6a, 14.3.4.6b and 14.3.4.6c).

This document is confidential.

11. Reference List

2. [SAS Program \(ages 0 to < 20 years \) | Resources | Growth Chart Training | Nutrition | DNPAO | CDC](#)

This document is confidential.

12. Programming Considerations

